| 10.1. | Data Collection | 31 |
| 10.2. | Data Confidentiality..... | 31 |
| 10.3. | Data Management | 32 |
| 10.4. | Data Use Agreements | 32 |
| 10.5. | Quality Assurance Metrics..... | 32 |
| 11. | PARTICIPANT RIGHTS AND CONFIDENTIALITY | 32 |
| 11.1. | Institutional Review Board (IRB) Review..... | 32 |
| 11.2. | Informed Consent..... | 32 |
| 11.3. | Participant Confidentiality | 33 |
| 11.4. | Study Discontinuation..... | 33 |
| 12. | ETHICAL CONSIDERATIONS..... | 34 |
| 13. | COMMITTEES | 35 |
| 14. | PUBLICATION OF RESEARCH FINDINGS..... | 35 |

15. REFERENCES..... 36
16 APPENDICES..... 44

PRÉCIS

Study Title: PROVEN: PRagmatic trial Of Video Education in Nursing homes

Objective: To conduct a pragmatic cluster randomized control trial (RCT) of an Advance Care Planning (ACP) video support intervention for nursing home (NH) patients ≥ 65 cared for in 360 NHs (intervention, n=119; control, n=241) within two NH health care systems; Genesis HealthCare and PruittHealth.

Design and Outcomes: Aim 1 of this study is to implement all aspects of a pragmatic cluster RCT trial of an ACP video support intervention in two NH health care systems, including: 1. Recruitment of a sufficient number of NHs to achieve the sample size of patients needed to demonstrate a clinically meaningful difference in the primary outcome; 2. Facility staff training and implementation of the intervention; and 3. Outcome assessment using EMR records, the Minimum Data Set (MDS), and Medicare Claims.

In this stratified cluster RCT, the unit of random assignment is the facility but the unit of analysis is the patient, clustered within the facility. The intervention will be implemented facility-wide, thus all patients cared for in the NHs during the 24-month implementation period are subjects in this study ($N \simeq 152,160$). However, outcomes will be analyzed in targeted sub-populations with advanced comorbid conditions for whom the opportunity and need to improve ACP and goal-directed care are greatest. These subgroups include very disabled older patients with advanced dementia and advanced congestive heart failure (CHF) or chronic obstructive pulmonary disease (COPD) (i.e., cardiopulmonary disease).

Outcomes to be compared between patients in the intervention and control NHs include: advance directives orders (Do Not Resuscitate (DNR), Do Not Hospitalize (DNH), Do Not Intubate (DNI), and no tube-feeding), hospital transfers, use of other burdensome interventions (new feeding tube insertions, parenteral therapy, intubation, ICU care), hospice use, and Medicare ACP billing codes. The effectiveness of the intervention to improve these outcomes among those targeted sub-populations with advanced illness will be assessed among long-stay (≥ 90 days) NH residents > 65 (Aim 2) and new admissions to post-acute care (short-stay < 90 days) (Aim 3). Finally, we will evaluate the effects of the intervention by examining the aforementioned outcomes among long-stay NH patients and new admissions who do NOT have either of the pre-specified advanced illnesses (Aim 4).

The primary outcome for this pragmatic trial is hospital transfers (quantified as number of hospital transfers/person-days alive based on Medicare claims data), which include admissions, emergency department visits, and observation stays over a 12-month follow-up period among long-stay residents with advanced dementia and/or advanced CHF/COPD. For all analyses involving this hospital transfer outcome, including the primary trial outcome, the main analyses will be restricted to Medicare Fee-for-Service patients because ascertainment of hospital transfers is most accurate from Medicare Claims data. Exploratory analyses will also be done on all patients, not just FFS, using the MDS as well as Medicare claims as the data sources. Secondary outcomes include advance directive orders, other burdensome treatments, and hospice use. An exploratory aim will be, among decedents, to compare the proportion of patients in the intervention and control facilities who had any of the following interventions in the last month of life: hospital transfer or other burdensome interventions (feeding tube insertion, parenteral therapy, intubation, ICU care).

Separate analyses will be done among decedents from the short and long-stay cohorts with advanced dementia, CHF or COPD, as well as those without advanced disease.

Interventions and Duration: The intervention consists of a suite of five videos designed to address common ACP decisions confronting NH patients and their families:

1. *Goals of Care for Any Patient*
2. *Goals of Care for Patients with Advanced Dementia*
3. *Decisions about Hospitalization*
4. *Decisions about Hospice*
5. *General Information about Advance Care Planning for Healthy Adults*

NHs randomized to the control arm of the study will use the usual ACP procedures already practiced in their facilities. The ACP Video Program will be implemented for 24 months in the intervention facilities. Individual patients in both arms who are in the NHs during the 24-month implementation period are eligible, and their outcomes will be assessed for up to 12 months in the long-stay cohort and 100 days in the short-stay cohort.

Sample Size and Population: The ACP video intervention will be implemented facility-wide in the NHs randomized to the intervention arm. Thus, ALL patients who are cared for during the 24-month implementation phase are potential participants in the trial and comprise the study population ($N \simeq 152,160$). However, the analyses described in Aims 2 and 3 will focus on target populations with advanced comorbid conditions that are cared for in the NHs during the 24-month implementation period. For Aim 2, the target sample is long-stay patients with advanced dementia or CHF/COPD ($N \simeq 14,760$). As the primary study trial outcome is hospital transfers in the long-stay patients, sample size estimates and power calculations are based on this target group. For Aim 3, the target sample is short-stay patients with advanced dementia or CHF/COPD. For Aim 4, the target sample is long-stay and short-stay NH patients who do NOT have either of the pre-specified advanced illnesses.

In this stratified cluster RCT, the unit of random assignment is the facility. Facilities will be randomized in the following strata in the following order: 1. Health care system (Genesis HealthCare and PruittHealth), and 2. Hospitalization rates in the 12 months prior to recruitment in target sub-populations (grouped as terciles). Outcomes analyses will not differ by strata.

STUDY TEAM ROSTER

Co-Principal Investigators:

[name], MPH

Senior Scientist, Institute for Aging Research, Hebrew SeniorLife,

Professor of Medicine, Harvard Medical School

<http://www.instituteforagingresearch.org/>

Address: [name]

[contact], [contact]

Email: [contact]

Main Roles: Member of Steering and Executive Committees; leader of Human Subjects and Data Safety and also Stakeholder Engagement working groups; management of team that coordinates all intervention implementation and training activities.

[name]

1. STUDY OBJECTIVES

Aim 1: To implement all aspects of a pragmatic cluster RCT trial of an ACP video support intervention in two NH health care systems, including: 1. Recruitment of a sufficient number of NHs to achieve the sample size of patients needed to demonstrate a clinically meaningful difference in the primary outcome; 2. Facility staff training and implementation of the intervention; and 3. Outcome assessment using EMR records, the Minimum Data Set (MDS), and Medicare Claims.

Aim 2: To evaluate the effectiveness of the ACP intervention by comparing the following outcomes over 12 months among long-stay NH residents ≥ 65 with advanced comorbid conditions (advanced dementia and/or advanced congestive heart failure (CHF) or chronic obstructive lung disease (COPD)) in the intervention vs. control NHs: 1. Advance directives to withhold specific treatments (DNH, DNR, DNI, and no tube-feeding), 2. Hospital transfers (# hospital transfers/person-days alive), 3. Other burdensome treatments (new feeding tube insertions, parenteral therapy, intubation, ICU care), 4. Hospice use, and 5. Medicare ACP billing codes.

H2a: A higher proportion of long-stay residents in the intervention (vs. control) NHs will have advance directive orders to withhold specific treatments over 12 months.

H2b: Over 12 months, hospital transfers (primary study outcome) and other burdensome interventions will be lower among long-stay residents in the intervention (vs. control) NHs.

H2c: A higher proportion of long-stay residents in the intervention (vs. control) NHs will be enrolled in hospice.

Aim 3: To evaluate the effectiveness of the ACP intervention by comparing the following outcomes in the intervention vs. control NHs among new admissions to post-acute care ≥ 65 with advanced comorbid conditions (as defined in Aim 2): 1. Advance directives to withhold specific treatments (DNH, DNR, DNI, no tube-feeding), 2. Hospital transfers within 100 days of the post-acute care admission (# hospital transfers/per-days alive), 3. Hospice enrollment within 100 days of the post-acute care admission, and 4. Medicare ACP billing codes within 100 days of the post-acute care admission.

H3a: A higher proportion of post-acute care patients in the intervention (vs. control) NHs will have advance directive orders to withhold specific treatments during their admission.

H3b: Hospital transfer rates will be lower among post-acute care patients in the intervention (vs. control) NHs.

H3c: A higher proportion of post-acute care in the intervention (vs. control) NHs will be enrolled in hospice.

Aim 4: To evaluate the effects of the ACP intervention by comparing outcomes (advance directive orders, hospital transfers, hospice use, and Medicare ACP billing codes) in the intervention vs. control NHs among long-stay residents and newly admitted post-acute care patients who do NOT have designated advanced illness (i.e., dementia, CHF, or COPD).

H4a: A higher proportion of NH patients without advanced dementia, COPD, or CHF in the intervention (vs. control) NHs will acquire advance directives to withhold specific treatments.

H4b: Hospital transfers will be lower among NH patients without advanced dementia, COPD, or CHF in the intervention (vs. control) arms.

H4c: A higher proportion of NH patients without advanced dementia, COPD, or CHF in the intervention (vs. control) NHs will be enrolled in hospice.

Exploratory Aim: Among decedents, to compare the proportion of patients in the intervention and control facilities who had any of the following interventions in the last month of life: hospital transfer or other burdensome interventions (feeding tube insertion, parenteral therapy, intubation, ICU care). Separate analyses will be done among decedents from the short and long-stay cohorts with advanced dementia, CHF or COPD, as well as those without advanced disease.

Cohort and outcomes specifications:

A. Hospital transfer outcome

1. For all analyses involving this outcome, including the primary trial outcome, the main analyses will be restricted to Medicare Fee-for-Service patients because ascertainment of hospital transfers is most accurate from Medicare Claims data. Exploratory analyses will also be done on all patients, not just FFS, using the MDS as well as Medicare claims as the data sources.
2. For the primary outcome and all relevant secondary outcomes, ‘hospitalizations’ was modified to ‘hospital transfers’ based on Medicare claims data, which include admissions, emergency department visits, and observation stays. This change was made so as to capture the main “decision” to send a patient from the nursing home to the hospital.

B. Advance directive outcome

1. For all aims, advance directives analyses will be limited to Genesis facilities in which >75% of patients have any advance directive because the remaining Genesis and Pruitt facilities do not have reliable sources for these data.
2. The proportion of residents in a facility whose last observed advance directive status during their observation period was DNR, DNH, DNI or feeding restrictions
 - i. The proportion of short-stay residents in a facility whose last observed advance directive status during their 100-day observation period was DNR, DNH, DNI or feeding restrictions
 - ii. The proportion of long-stay target residents in a facility whose last observed advance directive status during their 12-month observation period was DNR, DNH, DNI or feeding restrictions
 - iii. The proportion of long-stay non-target residents in a facility whose last observed advance directive status during their 12-month observation period was DNR, DNH, DNI or feeding restrictions
3. Among participants who are full code when they become part of the study (on admission to a NH), the average time to switching from full code to DNR, DNH, DNI or feeding restrictions during a 12-month observation period.

C. Burdensome interventions

1. For Aim 2.3, burdensome interventions will include: new feeding tube insertions (i.e., did not have a feeding tube at start of observation period), parenteral therapy (for hydration or medication delivery), intubation, or ICU care). The outcome will be analyzed as the proportion of long-stay target cohort residents that had any burdensome intervention during the 12-month observation period.

D. Hospice:

1. In the long-stay target cohort, the proportion of residents with any Medicare hospice claim in the 12-month observation period.
2. In the non-target long-stay cohort, the proportion of residents with any Medicare hospice claim in the 12-month observation period.
3. In the short-stay cohort without advanced comorbid conditions, the proportion of residents with any Medicare hospice claim in the 100-day observation period.
4. In the short-stay cohort with advanced comorbid conditions, the proportion of residents with any Medicare hospice claim in the 100-day observation period. For both long-stay and short-stay cohorts, residents on hospice at the start of the observation period will be excluded.

E. Medicare Advance Care Planning Billing

1. In long-stay target cohort, the proportion of residents with any Medicare ACP billing code in the 12-month observation period.
2. In non-target long-stay cohort, the proportion of residents with any Medicare ACP billing code in the 12-month observation period.
3. In short-stay cohort (with and without advanced comorbid conditions), the proportion of patients with any Medicare ACP billing code in the 100-day observation period.

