7.2. Serious Negative Reactions and Serious Adverse Events

The potential *serious negative reaction (SNR)* that could occur during this trial is serious distress by patients or family members in the intervention NHs while viewing an ACP video. As described in *Section 7.1.*, we anticipate that such SNRs will be exceedingly rare. Nonetheless, serious distress by may be manifested as a very negative emotional reaction while watching or after watching a video, asking for the video to be stopped, or leaving the room while a video is being shown. Due to the sensitive nature of the material, tearing up by the proxy can be expected and is not deemed to be a reflection of distress.

We do not believe that there are any potential consequences of this trial that meet the definition of *serious adverse events (SAEs)*.

(We do not believe death should be considered a SAE for the PROVEN trial for the following reasons. First, the study is being conducted in a frail NH population with advanced illnesses. Thus,

death is often not an unexpected event in their clinical course. Second, all NHs must engage patients and families in ACP as part of routine clinical practice. The videos are meant as an adjunct to facilitate ACP counseling. The underlying intent of all ACP, regardless of how it is done, is to help patients make informed treatment decisions so they receive care that is concordant with their preferences. For patients who prefer comfort or palliation as a main goal of care (vs. life prolongation), death is not an adverse outcome. Finally, it is not known whether more aggressive care (i.e., hospitalization) would result in greater mortality compared to less aggressive care (i.e., conservative or palliative treatment on-site in the NH). Therefore, while we hypothesize that there will be fewer hospitalizations among NH patients with advanced disease randomized to the intervention arm (vs. control), it is impossible to predict how this may impact mortality rates.)

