9. STATISTICAL CONSIDERATIONS

9.1. General Design Issues

PROVEN is pragmatic cluster RCT of an ACP Video Program intervention for NH patients cared for in two NH health care systems: Genesis HealthCare and PruittHealth. Rationale for this choice of study design is provided in Section 2.6. The intervention will be implemented facility-wide; thus, all patients in the NHs during the 24-month implementation period comprise the study population. However, the analytic plan focuses on the effect of the ACP Video Program vs. control in the following targeted patient sub-groups:

- Long-stay residents (≥ 90 days) with advanced dementia or advanced CHF/COPD (Aim 2)
- Short-stay patients (< 90 days) with advanced dementia or advanced CHF/COPD (Aim 3)
- Long and short-stay patients without these advanced illnesses (Aim 4).

The primary trial outcome is hospital transfers (number of hospital transfers/person-days alive based on Medicare claims data), which include admissions, emergency department visits, and observation stays over a 12-month follow-up period among Medicare fee-for-service long-stay residents with advanced dementia or advanced CHF/COPD. The primary hypothesis is that the rate of hospital transfers will be lower in the intervention group.

Secondary outcomes include hospital transfer rates in the sub-groups examined in Aims 3 and 4, and the following outcomes for all sub-groups in Aims 2, 3 and 4: advance directives, burdensome treatments, hospice use, and Medicare ACP billing codes.

Each long-stay resident will be followed for up to 12 months starting from the date they are first identified as meeting our target cohort definition during the 24-month intervention period and short-stay patients will be followed for 100 days from their NH admission date. The analytic approach to Aims 2, 3, and 4 are similar. Analyses begin with descriptions of all major variables using frequencies and means/medians with SDs/interquartile ranges, as appropriate. Outcomes will be compared between the control and intervention arms using a zero-inflated Poisson model

with random effects to account for clustering at the NH level. While we do not anticipate an effect on mortality, analyses will also examine the effects on mortality. Primary analyses will follow the intention to treat principle and will adjust for minor imbalances in patient characteristics, as needed.

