9.5. Data Analyses

Aim 1: To implement all aspects of a pragmatic cluster RCT: Assessment of Aim 1 will largely be experiential and based on meeting planned recruitment milestones. We will assess the implementation of the ACP Video Program by examining data from the new Video Status Report

User Defined Assessment record created in the EMR that documents the videos offered. Descriptive statistics will be generated describing the proportion of the general NH population and targeted sub-populations exposed to the video, which videos they saw, who saw them (patient and/or family members), who showed the videos (nurse, physician, social worker), and the timing of exposure (i.e., relative to admission, discharge care planning meetings).

Aim 2 To evaluate the effectiveness of the ACP intervention among long-stay NH residents with advanced comorbid conditions: The sample includes long-stay residents with advanced dementia and advanced CHF/COPD. The primary trial outcome is the hospital transfer rate (number transfers/person-days alive based on Medicare claims data), which include admissions, emergency department visits, and observation stays) over a 12-month follow-up period among Medicare fee-for-service) in this cohort. Secondary outcomes include: advance directives (DNR, DNH, DNI, no tube-feeding), burdensome treatments (new feeding tube insertion, intubation, parenteral therapy, ICU care), hospice admission, and Medicare ACP billing codes. All outcomes will be 12-month incidence measures starting from the date residents are first identified as meeting the criteria for definitions of having advanced dementia or CHF/COPD during the 24-month intervention period. While we do not anticipate the ACP intervention to affect mortality,³¹ our analyses will account for censoring during the 12-month observation period. We will formally test for a mortality differential between intervention and controls arms using a logistic regression random effects model, where clustering is performed by facility.

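### The exploratory end-of-life comparison is restricted to residents who died, a group formed after randomisation that the intervention could change in either direction, and nothing in the plan restores comparability for it

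*Combined protocol and SAP*

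**What the plan says.** The Précis and Section 1 both restrict the exploratory aim to residents who died. Section 1 states it as "Among decedents, to compare the proportion of patients in the intervention and control facilities who had any of the following interventions", and the list of interventions is those "in the last month of life: hospital transfer or other burdensome interventions (feeding tube insertion, parenteral therapy, intubation, ICU care"). The strata, which also cover residents free of the advanced illnesses, do not change the restriction: "Separate analyses will be done among decedents from the short and long-stay cohorts with advanced dementia, CHF or COPD, as well as those without". The Précis labels the aim exploratory. It carries no directional hypothesis, unlike Aims 2 to 4.

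On mortality the plan says three things. Section 7.2, explaining why death is not treated as a serious adverse event, says of fewer hospitalizations that "it is impossible to predict how this may impact mortality rates". Section 9.1 says: "While we do not anticipate an effect on mortality, analyses will also examine the effects on mortality". Section 9.5 repeats that no effect is expected and, under Aim 2, adds: "We will formally test for a mortality differential between intervention and controls arms using a logistic regression random effects model".

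Section 9.5 gives no method for the decedent aim. It has no adjustment, sensitivity analysis or caveat about selection into the decedent group, and no rule for reading that aim in the light of the mortality result.

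**The concern.** Randomisation makes the arms comparable at the start of follow-up. It does not make those who later die comparable, unless the intervention leaves unchanged who dies within the window. The intervention aims to reduce transfers, and forgoing transfer is one route by which it could alter both who dies and how that death is classified.

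Suppose some intervention residents stay in the home and die when they would otherwise have been transferred and survived. They enter the decedent denominator mostly as cases without an event, and the proportion falls although nobody who would have died anyway was treated differently. If instead some deaths without an event are delayed beyond the window, the proportion rises. A difference between decedent groups therefore cannot be attributed to a change in end-of-life care. In a trial of comfort-oriented planning, a lower figure is easily read as better care at the end of life.

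**Working it through.** The plan gives no rate, effect or power for the decedent comparison, so there is no figure to reproduce. What follows is an illustration for the long-stay target cohort.

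**Inputs from the documents.** 119 intervention and 241 control facilities. About 41 target residents per facility (14,760/360 = 41; Section 9.2 uses 42, which leaves the 3-point result below at 47%). Main analyses of hospital transfers are restricted to fee-for-service residents (Section 1).

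**Assumptions, not in the documents.** 70% fee-for-service; control mortality m = 0.40 over 12 months; event proportion among control decedents p = 0.50; ICC 0.03 for the event. The plan's only mortality figures are for post-acute patients over 6 months (nearly 50% and 30%, Section 9.5, Aim 3), which is a different cohort. The plan attaches no test to this aim; the P<0.05 figures show what a two-sided 5% test would do.

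**Step 1: shift.** Let x be the added deaths and q the share of them with an event, with nothing else changed. The intervention decedent proportion is (m·p + x·q)/(m + x).

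- x = 0.01, q = 0: 0.20/0.41 = 0.488, a fall of 1.2 points.
- x = 0.03, q = 0: 0.20/0.43 = 0.465, a fall of 3.5 points.
- x = 0.03, q = 0.25: 0.2075/0.43 = 0.483, a fall of 1.7 points.
- Opposite direction, 3 points of event-free deaths moved outside the window: 0.20/0.37 = 0.541, a rise of 4.1 points.

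**Step 2: chance of P<0.05.** For x = 0.03, q = 0:

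- Decedents per facility: 0.7 × 41 × 0.43 = 12.34 (intervention) and 0.7 × 41 × 0.40 = 11.48 (control), giving 1,469 and 2,767 in total.
- Design effects 1 + (c − 1) × 0.03, with c decedents per facility: 1.340 and 1.314.
- SE = √(0.465 × 0.535 × 1.340/1,469 + 0.25 × 1.314/2,767) = 0.0186.
- Φ(0.0349/0.0186 − 1.96) = 0.47.

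The same steps give about 0.10 for x = 0.01, q = 0 and 0.15 for x = 0.03, q = 0.25.

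**Step 3: would the mortality test reveal it?** Using all target residents (119 × 41 = 4,879 and 241 × 41 = 9,881) and an assumed ICC of 0.02, the design effect is 1 + 40 × 0.02 = 1.80. At 40% mortality, SE = √(0.24 × 1.80 × (1/4,879 + 1/9,881)) = 0.0115. Power is Φ(0.03/0.0115 − 1.96) = 0.74 for 3 points and Φ(0.01/0.0115 − 1.96) = 0.14 for 1 point. Over mortality of 30% to 50% it is about 72% to 80% for 3 points and 40% to 46% for 2 points.

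**Step 4: equal death rates are not enough.** If total mortality is identical but 5% of decedents are exchanged from a type with 60% events to a type with 10%, the proportion falls by 0.05 × (0.60 − 0.10) = 2.5 points. No mortality test can detect that.

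**Step 5: same scenario, full cohort.** With x = 0.03 and q = 0, died with an event is 0.40 × 0.50 = 20% in both arms. Died without one is 20% in control and 23% in intervention. The decedent-only fall of 3.5 points is then seen for what it is.

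**The case against.** The case against has substance. The aim is exploratory, with no stated test or causal claim, and no primary or secondary conclusion depends on it. The plan does not expect a mortality effect. Section 2.2 describes an earlier nursing-home trial with fewer hospitalizations and no change in survival, and Section 2.3 says common precipitating illnesses can usually be treated as effectively in the home. Mortality will be examined, death is listed as a competing risk in Table 2, and transfers and burdensome interventions are analysed over 12 months in the whole long-stay target cohort.

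The larger shifts are also demanding. Section 9.6 reports that only 12.5% and 31.4% of long-stay residents in the two systems had been shown a video. If effects run mainly through viewing, 3 added points of deaths means 0.03/0.125 = 24 or 0.03/0.314 = about 10 extra deaths per 100 residents shown; 1 point means 8 or about 3. Online viewing and facility culture could add exposure. Parenteral therapy counts as an event, so residents who forgo transfer need not be event-free.

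All of this limits the size and importance of the point, and the lower end of the range deserves more weight. It does not remove the point. An expectation of no mortality effect is not protection, the whole-cohort analyses measure 12-month use and not care before death, and Step 4 applies even when mortality is equal. The formal mortality test is described only under Aim 2, while the decedent aim also covers short-stay residents and those without advanced disease.

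**Conclusion.** The point holds as a limit on interpretation that is cheap to remove. The decedent-only contrast is not protected by randomisation, and the plan neither says so nor offers a protected counterpart. Under the stated assumptions, 1 to 3 added points of event-free deaths would produce an apparent reduction of 1.2 to 3.5 points (P<0.05 in about 10% to 47% of trials), or 1.7 points (15%) if a quarter of 3 added points had an event.

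A reader might infer more: that the aim will produce a false benefit, that 47% is the likely error rate, or that the main result is compromised. The documents support none of these. They give no evidence that mortality will change or in which direction, the upper figure needs 3 added points of wholly event-free deaths despite low reported viewing, and the primary outcome uses the whole long-stay target cohort per person-day alive. It would also be wrong to say the plan ignores mortality; it plans to test it, but that test does not make this contrast comparable.

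**What to change.** In the Exploratory Aim (Section 1 and Précis), with a matching paragraph in Section 9.5, add two full-cohort binary outcomes for each cohort:

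- (a) died in the observation period with a hospital transfer or burdensome intervention in the last month of life;
- (b) died in the observation period without one.

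Analyse both with the random-effects logistic model already specified for secondary outcomes. Show them beside the mortality comparison for the same cohort and the same denominator, so that (a) and (b) add up to mortality. This means reporting mortality by arm for the short-stay cohorts and those without advanced disease too. Keep the decedents-only proportion as a descriptive supplement, stated not to be a randomised comparison.

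The cost is SAP wording and recoded binary outcomes; no new data are needed. The downside is that full-cohort percentages are smaller and less familiar than percentages of decedents. Keeping the decedent figure as description meets that need.
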